1 PROTOCOL SYNOPSIS

Study title	Metformin continuation safety in diabetic patients undergoing coronary			
•	angiogra p hy.			
Acronym	NO-STOP			
IRCCS internal sites:	Cardio Center, IRCCS Istituto Clinico Humanitas – [name]			
IRCCS external sites:	None			
Population	Diabetic patients treated with metformin undergoing coronary angiography.			
Objectives	To assess the safety of metformin in diabetic patients undergoing coronary angiography in terms of risk of lactic acidosis. Individuate eventual clinical, echocardiographic predictors of lactic acidosis in this setting.			
Study design	Prospective, no-profit, single arm trial, powered for non-inferiority with respect to historical cohort.			
Sample size	The study require the enrollment of at least 110 patients.			
Primary endpoint	Increase of 20% from preprocedural lactic acid values.			
Secondary endpoints	Contrast-associated acute kidney injury after coronary angiography. Lactic acidosis development after coronary angiography. Correlation between clinical, laboratoristic, and echocardiographic variables and lactic acid values.			
Inclusion criteria	Diabetic patients treated with metformin undergoing coronary angiography.			
Exclusion criteria	Known coronary anatomy with planned complex percutaneous coronary intervention with high probability of large amount of contrast use (>150 ml). Moderate to severe impairment of renal function (eGFR<45 ml/min). Moderate to severe impairment of liver function (Child-Pugh class B or C). Severely impaired left ventricular ejection fraction (LVEF <35%). Patients undergoing primary percutaneous coronary intervention (i.e., patients presenting with ST elevation myocardial infarction). Severe to very severe chronic obstructive pulmonary disease (GOLD class 3 to 4). Patients scheduled for cardiac surgery in the following 5 days. Inability to provide informed consent.			
Prespecified	Patients taking other antiglycaemic drugs on top of metformin.			
subgroup analyses	Patients requiring percutaneous coronary angioplasty. Patients with mild and moderate renal function impairment (eGFR<90 and <60 ml/min). Patients undergoing urgent coronary angiography (<24 hours from the index event).			
Follow-up	The days after coronary angiography, at discharge and after three days from coronary angiography.			

CONFIDENTIAL

1.1. TIME SCHEDULE

Event	Screening	Post-procedure	At discharge	At three days
Type of contact with the patient	Visit		Visit	Visit/phone call
Inclusion/exclusion criteria	х			
Informed consent	х			
Medical hystory	х			
Physical examination	х	х	х	
Hemocrome, kidney and liver function, lactic acid	х	х	х	х
CK-MB, hs-troponin I, BNP	х	х	x	
Transthoracic echocardiography	х			
12-leads electrocardiogram	х	х	x	
Lactic acidosis, death, kidney failure, liver failure		Х	х	Х

NO-STOP protocol

CONFIDENTIAL

2. BACKGROUND

Metformin is an antiglycemic drug member of biguanide class, firstly introduced in 1957 for the treatment of non-insulin dependent diabetes mellitus. It is the most widely prescribed drug for glycemic control in diabetic patients and it is often used in combination with other antiglycemic drug and insulin.^{1,2} Its mechanism of action depends on decreased hepatic gluconeogenesis and glycogenolysis,³ and increased skeletal muscle glucose uptake.⁴ Moreover, metformin is also associated with a reduction in cardiovascular morbidity and mortality, when compared to insulin or sulfonylureas.⁵ Diabetes mellitus is extremely common among patients with coronary artery disease, with prevalence reaching 40% in some reports of patients undergoing percutaneous coronary intervention.⁶ Therefore, metformin is one of the most common drug prescribed to patients with indication for coronary angiography. Notwithstanding, the biguanide agent that preceded metformin, phenformin, was withdrawn from clinical practice in 1978, due to an unacceptable risk of lactic acidosis, ranging from 40 to 64 cases per 100,000 patient-years.⁷ However, metformin present different pharmacokinetics and pharmacodynamics properties, with an estimated risk of lactic acidosis ten to twenty times less than that of phenformin. Considering the high risk of lactic acidosis with its predecessor phenformin and the high mortality of this condition, the vast majority of physician used to suspend metformin before contrast use.⁸

The incidence of lactic acidosis after metformin has recently come into question, while it has been recognized that the routinely discontinuation of metformin could carry the converse risk of deleterious effects on glycemic control, increased cardiovascular and acute kidney injury risk.⁹ Metformin itself is not directly nephrotoxic,¹⁰ but in patients predisposed to acute deterioration in renal function after contrast administration, i.e., contrast-induced nephropathy (CIN), it has been postulated that there is the potential for metformin to accumulate, leading to lactic acidosis. However, evidence for this is totally lacking.^{8,11} Firstly, although CIN occurs in 2% to 25% of patients undergoing coronary intervention,¹² not every patient on metformin that develops CIN develops lactic acidosis.¹³ Secondly, most of the reported cases of lactic acidosis in patients taking metformin have been in patients with severe underlying conditions, including renal dysfunction, septicemia, hepatic failure and acute left ventricular failure, any of which could in themselves contribute to the lactic acidosis.^{14–16}

3. POTENTIAL RISKS AND BENEFITS

The present study aims to evaluate the strict application of the 2018 European Society of Cardiology on myocardial revascularization, that recommends to check renal function if patients have taken metformin immediately before angiography and withhold metformin if renal function deteriorates.¹¹ A recent meta-analysis, using pooled data from 347 prospective comparative trials and observational cohort studies, found no cases of fatal or non-fatal lactic acidosis in 70,490 patient-years of metformin use nor in 55,451 patient-years in the non-metformin group.¹⁷ Using Poisson statistics with 95% confidence interval the authors reported that the upper limit for the incidence of lactic acidosis in patients taking metformin was 4.3 cases per 100,000 patient-years, and in the non-metformin group the upper limit for the incidence of lactic acidosis was 5.4 cases per 100,000 patient-years. The risk for acute kidney injury in patients undergoing angiographic procedure with those preventive measures constantly applied in our center is considered to be the same of those patients not undergoing procedure without iodinated contrast medium. Moreover, we will

exclude from the study all those patients considered at augmented risk of CIN.^{10,12} Therefore, we assume that the risk for lactic acidosis in our expected population is the same that patients have with their everyday metformin assumption.

Moreover, considering the documented augmented risk of hyperglycemia in patients suspending metformin for angiographic procedure,⁸ and the augmented risk of serious adverse events in patients with hyperglycemia,¹⁸ there could be the advantage of maintaining the usual antiglicemic therapy including metforminthat should be probably more appropriate than an empiric insulin regimen started at hospital admission.

4. STUDY OBJECTIVES

Assess the safety of metformin in diabetic patients undergoing coronary angiography in terms of risk of lactic acidosis. Individuate eventual clinical, echocardiographic predictors of augmented lactic acid after coronary angiography.

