7. ENDPOINTS

7.1. Primary endpoint

An increase of lactic acid of 20% from preprocedural values in patients undergoing coronary angiography without discontinuing metformin.

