11.2. Level of significance

Statistical test will be used to:

- to refuse the null hypothesis of lack of association between metformin continuation and postprocedural increase of lactic acid of 20% from baseline values (primary endpoint) and our secondary endpoints (Ho = metformin continuation not associated with the endpoint)

Association between variables or events will be set at probabilistic level of 5% (p value< 0.05)

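### The objective is safety in terms of lactic acidosis risk, but the study is designed and sized only for a change in lactate; zero acidosis cases is almost certain and would exclude only a risk above about 3%

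*Combined protocol and SAP*

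**What the plan says.** Section 4 gives the objective as "Assess the safety of metformin in diabetic patients undergoing coronary angiography in terms of risk of lactic acidosis". The synopsis carries the same safety objective and adds a second: "Individuate eventual clinical, echocardiographic predictors of lactic acidosis in this setting". The matching sentence in Section 4 names a different target: "Individuate eventual clinical, echocardiographic predictors of augmented lactic acid after coronary angiography".

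The rest of the plan is about lactate:

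- The primary endpoint (Section 7.1) is "An increase of lactic acid of 20% from preprocedural values in patients undergoing coronary angiography without discontinuing metformin".
- Section 8.1 sizes the study (106 patients, 90% power, alpha 0.05) for that 20% rise. The synopsis says "The study require the enrollment of at least 110 patients".
- Section 9 states the aim as finding out whether continuing metformin raises lactic acid.
- Section 11.1 promises confidence intervals for post-procedure lactic acid and a linear regression on those values.

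Lactic acidosis is a secondary endpoint (Section 7.2). It has no definition, acceptable upper limit or precision target. Section 3 reports from a meta-analysis that "the upper limit for the incidence of lactic acidosis in patients taking metformin was 4.3 cases per 100,000 patient-years", and assumes the study population has the same risk as in everyday use. Section 11.2 applies the 5% test to the primary endpoint "and our secondary endpoints (Ho = metformin continuation not associated with the endpoint". Section 5 describes a single arm, and the last scheduled contact is at three days.

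**The concern.** The objective names one quantity and the design measures another. A study of 106 to 110 patients followed for three days says little about an event as rare as the one Section 3 describes. If the objective stands as worded, the report has to answer a lactic acidosis question with a count that was almost certain to be zero before the first patient was enrolled. A non-significant result from the Section 11.2 test could then be taken as evidence of no association, although that test has almost nothing to work with. What is at stake is the headline conclusion. The lactate analysis itself is not affected.

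**Working it through.** **Inputs from the documents.** n = 110 (synopsis) or 106 (Section 8.1). Lactate mean 1.2 and SD 0.7 mmol/l, 20% rise, 90% power, alpha 0.05 (Section 8.1). Follow-up three days (synopsis, Section 1.1). No cases in 70,490 patient-years on metformin, upper limit 4.3 per 100,000 patient-years (Section 3). Phenformin rate up to 64 per 100,000 patient-years (Section 2).

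**Assumptions.** The SD of the within-patient change is not given; 0.7 is used. Each patient is at risk for the full three days.

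**1. The plan's sample size.** The rise to detect is 0.20 × 1.2 = 0.24 mmol/l. For a two-sided one-sample test on the change, n = (0.7 × (1.960 + 1.282) / 0.24)² = 89.4, so 90; the t-test version gives 92. Building the minimum signed-rank efficiency of 0.864 into the t-test calculation gives 106. So does 90 / 0.85 = 105.9, a 15% dropout allowance that the protocol does not state. Which route was used is not stated. Either way 106 is a lactate figure, and acidosis plays no part in it.

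**2. The plan's acidosis rate.** A one-sided 95% Poisson limit for zero cases is −ln(0.05) / 70,490 = 2.996 / 70,490 = 4.25 per 100,000. The rule of three, 3 / 70,490, gives 4.26. Both agree with the quoted 4.3 to within rounding. The 4.3 is therefore an upper limit, and the expected count below is a ceiling under the protocol's own assumption.

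**3. Expected cases.** Exposure is 110 × 3 / 365.25 = 0.903 patient-years. Expected cases are 0.903 × 4.3 / 100,000 = 0.000039, so the chance of seeing even one is about 0.004%. At the upper phenformin rate the expectation is 0.903 × 64 / 100,000 = 0.0006. Zero cases would look the same under either drug's cited rate.

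**4. What zero cases would exclude.** The exact upper limit is 1 − a^(1/n), with a = 0.05 (one-sided) or 0.025 (two-sided).

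| n | One-sided 95% | Two-sided 95% |
|---|---|---|
| 110 | 2.7% | 3.3% |
| 106 | 2.8% | 3.4% |

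**5. If the procedural risk were higher than Section 3 assumes.** The chance of at least one case in 110 is 1 − (1 − p)^110. For illustrative risks p it is 1.1% at 0.01%, 10% at 0.1% and 67% at 1%. A true risk of 1 in 1,000 would still give zero cases about 90% of the time.

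**6. Could more patients solve it?** With no events, a one-sided upper limit of 1% needs 299 patients (ln 0.05 / ln 0.99 = 298.1), and 0.1% needs 2,995.

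**7. The test in Section 11.2.** Its null hypothesis concerns association with continuing metformin, but every patient in the single arm is to continue it. The synopsis mentions a historical cohort. Section 8.1 describes that cohort as taking metformin and gives only its lactate mean and SD. No group that stopped metformin, and no comparator acidosis count, is described.

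**8. The predictor objective.** The synopsis says "predictors of lactic acidosis in this setting". Section 4, the third secondary endpoint and the regression in Section 11.1 all concern lactic acid values. The synopsis phrase is the only one out of line, and no analysis corresponds to it.

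**The case against.** The strongest reply is that the protocol already does most of what is asked. Section 9 states a lactate aim; the endpoint, sample size, intervals and regression follow it; and a rare clinical event carried as an unpowered secondary safety endpoint is common practice and no defect in itself. That stands, and it confines the problem to the objective wording in two places and the reach of the test in Section 11.2.

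Several stronger readings are tempting, and the documents do not support them:

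- *The study cannot bound the risk at all.* It can: zero cases gives a limit of about 3%. The limit is simply far above the risk the protocol has in mind.
- *The plan contains a safety claim that zero events would satisfy.* No success rule for lactic acidosis is written. That zero cases, or a non-significant test, would be taken as safety is a risk of the objective's wording, not something the plan states.
- *A predictor model for lactic acidosis is planned and cannot be fitted.* Section 11.1 plans only a linear regression on lactic acid values.
- *The 5% test cannot be computed without events.* The Fisher test that Section 11.1 allows is defined with no events and returns p = 1. It is uninformative, not impossible.
- *The study's limit is some 77,000 times the cited rate.* The arithmetic is 2.996 / 0.903 patient-years, about 332,000 per 100,000 patient-years, divided by 4.3. This annualises a three-day procedural window and sets it against long-term use. The per-patient limit of about 3% is the relevant figure.

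**Conclusion.** The point holds in this form. The objective in Section 4 and the synopsis is one that the design cannot usefully answer, while the lactate question can be answered with the planned sample. On the protocol's own rate about 0.00004 cases are expected, and zero cases would exclude only a per-patient risk above about 3% (2.7% to 3.4%, depending on n and sidedness). The test in Section 11.2 adds no information on lactic acidosis, for two separate reasons: almost no events are expected, and no comparator stopped metformin. The second reason applies whatever the event count.

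The expected count rests on Section 3's assumption of everyday risk and on three days at risk. The 3% limit needs neither. The difference between 106 and 110 patients is a separate inconsistency and does not change the conclusion. This should be corrected because it decides what the trial may conclude, but it does not undermine the primary analysis.

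**What to change.** - **Section 4 and synopsis, objective:** restate it as the change in lactic acid after angiography with metformin continued, as Section 9 already does.
- **Synopsis, predictor objective:** change the target to predictors of post-procedure lactic acid, to match Section 4 and the regression in Section 11.1.
- **Section 11.2:** drop the significance test for lactic acidosis. Report it as a count with an exact 95% confidence interval.
- **Section 7.2:** state the definition of lactic acidosis behind that count. The scheduled laboratory tests list lactic acid but no pH or blood gas, so the definition must either fit the samples collected or name what is added.
- **Interpretation:** state in advance that zero cases excludes only a risk above about 3% and does not by itself establish safety for lactic acidosis.

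The cost is wording in these sections and one interval, with no extra patients. No new procedure is needed unless the chosen definition requires a further measurement. The downside is a narrower headline claim.

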5. STUDY DESIGN

The study is designed as a prospective, observational, single arm study.

Enrollment timing: enrollment rate will determine the duration of the study. We estimate that one year will be sufficient to achieve this objective.

Enrollment center: the study will be conducted at the Cardiac Center of the Humanitas Research Hospital, [name].

7. ENDPOINTS

7.1. Primary endpoint

An increase of lactic acid of 20% from preprocedural values in patients undergoing coronary angiography without discontinuing metformin.

7.2 Secondary endpoints

Contrast-associated acute kidney injury after coronary angiography.

Lactic acidosis development after coronary angiography.

Correlation between clinical, laboratoristic, and echocardiographic variables and lactic acid values.

8. STUDY POPULATION

8.1. Sample size

In our historical cohort of diabetic patients taking metformin, we observed a mean value of lactic acid of 1.2+0.7 mmol/l.

A total of 106 patients in an estimated time of one years are planned to be enrolled in order to detect with 90% power a prespecified increase of lactic acid of 20% from preprocedural values with a probability of alpha error of

0.05.

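### The synopsis claims non-inferiority to a historical cohort whose metformin use around angiography is not stated, and nothing in the design can separate continuing metformin from suspending it

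*Combined protocol and SAP*

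**What the plan says.** The synopsis (section 1, study design row) describes the study as "Prospective, no-profit, single arm trial, powered for non-inferiority with respect to historical cohort". Section 5 drops the non-inferiority element: "The study is designed as a prospective, observational, single arm study".

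The cohort appears once more, in section 8.1: "In our historical cohort of diabetic patients taking metformin, we observed a mean value of lactic acid of 1.2+0.7 mmol/l". The same section sizes the study to "detect with 90% power a prespecified increase of lactic acid of 20% from preprocedural values with a probability of alpha error of" 0.05, and states: "A total of 106 patients in an estimated time of one years are planned to be enrolled".

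Section 7.1 defines the primary endpoint as a 20% rise in lactate over the patient's own preprocedural level, in patients who do not stop metformin. Section 9 gives the aim as finding out whether continuing metformin could raise lactate. The null hypothesis in section 11.2 is that continuation has no association with the endpoint. Section 11.1 lists general tests, subgroups and a regression; it contains no comparison with the cohort and no non-inferiority margin.

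On the practice in question, section 2 says that "the vast majority of physician used to suspend metformin before contrast use", and section 3 argues that keeping the usual therapy may be preferable to suspending it.

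**The concern.** The background sets continuing metformin against suspending it before contrast. A non-inferiority claim in that setting will be read as saying that continuing is no worse than stopping. To support that reading, the study needs patients whose metformin was held, or a comparator whose handling of metformin is known. The plan describes neither.

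Two references are also in play. The synopsis points to the cohort; the endpoint and the power statement point to the patient's own baseline. If the results are reported under the synopsis wording, a small rise in lactate could be presented as non-inferiority to a group that was never formally compared and whose exposure is unknown. A large rise could be blamed on metformin when the procedure, the contrast or the acute illness caused it.

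**Working it through.** **1. What each reference can identify**

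| Reference | Where | Metformin status | What a comparison would show |
|---|---|---|---|
| Historical cohort | Synopsis; section 8.1 | Takes metformin; whether held around a procedure is not stated | Study patients against a group of unknown timing, procedure status and case-mix |
| Own preprocedural value | Sections 7.1, 8.1, 11.2 | On metformin before, and not stopped for the procedure | Lactate change across angiography under continuation |
| Patients with metformin suspended for the procedure | Nowhere | – | Would be needed for continuing versus suspending |

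For a patient who continues, the change in lactate is the sum of (a) the change that would have occurred with metformin suspended and (b) the extra change due to continuing. The study observes only the sum. With no variation in exposure, (a) and (b) cannot be separated, so an association between continuation and the endpoint cannot be estimated. Section 10.2 has patients who develop contrast nephropathy stop metformin. That follows from an outcome of the procedure, so it does not supply a comparator.

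**2. Which reference the sample size fits**

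Inputs from section 8.1: mean 1.2 and SD 0.7 mmol/l (reading the plus sign as plus/minus), a 20% rise, 90% power, alpha 0.05. Sidedness, test and dropout are not stated; two-sided is assumed.

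- Target difference: 0.20 × 1.2 = 0.24 mmol/l. Standardised: 0.24 / 0.7 = 0.343.
- One-sample or paired, normal approximation: n = [(1.960 + 1.2815) × 0.7 / 0.24]² = 89.4, so 90. The noncentral t gives 92.
- Signed-rank test at its minimum asymptotic relative efficiency of 0.864: n = 106, power 0.901. This reproduces the stated figure. So does 90 / (1 − 0.15) = 105.9, rounded up to 106.
- Two equal groups: n = 2 × 89.4 = 178.8, so 179 per group (358 in total). This is not 106.
- Against a larger cohort with k cohort patients per study patient: n = 89.4 × (1 + 1/k). This gives 108 at k = 5 and 99 at k = 10.

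The figure of 106 therefore fits a within-patient test or a test against a fixed value. It does not fit an equal-group comparison. A cohort somewhat more than five times the study's size would also give about 106, but no cohort size is stated, so the figure alone does not settle the route. The section 8.1 wording, which refers to preprocedural values, favours the within-patient reading.

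These sums treat 0.7 as the SD of the change. If it is the SD of single values, that holds only at a pre/post correlation of 0.5. Assumed correlations of 0.3 to 0.7 give an SD of change of 0.83 to 0.54.

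**3. What a real comparison would take (illustration)**

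With the same difference and SD, a concurrent suspended group needs 179 per group for 90% power at two-sided 0.05. With 106 per group power is 70%; with 106 split into 53 and 53 it is 42%.

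**4. Sensitivity of a direct cohort comparison**

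The target effect is 0.24 mmol/l, or 0.34 of the cohort SD. A difference of that size in mean lactate due to case-mix or sampling time would match the whole effect. The documents give no information on how large such a difference might be.

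**The case against.** The strongest reply is that no cohort comparison is planned. The endpoint, the power statement and section 11.2 all use the patient's own baseline, section 8.1 uses the cohort only to supply a mean and SD, and section 5 openly calls the study observational and single arm. On this view the non-inferiority clause is a stray phrase in the synopsis, and the objectives in section 4 ask about safety under metformin, not about continuing versus suspending. Much of this stands: the body of the protocol already works as a before-and-after study. It does not dispose of the point, because the synopsis still claims a property the design lacks, and the aim in section 9 and the hypothesis in section 11.2 still attribute any rise to continuation.

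A reader might also infer that the cohort had the same exposure as the study arm, or that it contained no suspended patients. The documents do not support either. Taking metformin can describe long-term treatment, and section 2 makes it plausible that doses were held around contrast. The cohort's periprocedural exposure is unstated; it has not been shown to be the same.

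**Conclusion.** The point holds as an inconsistency between the synopsis and the body, together with a limit on what the design can answer. The study can estimate the change in lactate across angiography in patients who continue metformin. It cannot show non-inferiority to the cohort as planned, since there is no margin, no specified comparison and no adequate description of the cohort. Nor can it show whether continuing rather than suspending raises lactate. The hypothesis in section 11.2 is untestable as worded because exposure does not vary.

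The 0.24 mmol/l figure applies only if the cohort is compared directly. It would be tempting to say that such an offset could create or cancel the primary result, but a difference between cohort and study patients does not enter a within-patient change. The conclusion about identifiability rests on the absence of any described suspended group and needs no numerical assumption. The sample-size reading rests on an inferred test and two-sided alpha.

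**What to change.** 1. **Synopsis, study design row:** delete the clause on non-inferiority power against the historical cohort. Keep the cohort in section 8.1 only as the planning source for the mean and SD.
2. **Sections 7.1 and 11:** state that each patient's preprocedural lactate is the sole reference for the primary endpoint.
3. **Sections 9 and 11.2:** reword the aim and the null hypothesis in terms of the change in lactate from before to after angiography in patients who continue metformin. Changing the synopsis alone would leave the causal question in these two places.
4. **Reporting:** limit the conclusion to that change, with no statement about continuing versus suspending.

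This costs wording and a less favourable headline; no extra patients or data are needed.

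A comparative claim would be a different and larger undertaking. A historical version would need past angiography patients whose metformin was held, who meet the same exclusions and who have lactate before and after, with changes compared rather than levels. Section 9 says lactate will be added to the routine tests around angiography, which suggests, without proving, that such data do not exist. A concurrent version would need about 179 per group on the plan's own inputs.

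### The synopsis claims non-inferiority to a historical cohort with at least 110 patients; the body plans 106 to detect a 20% rise, gives no margin or cohort comparison, and does not show how 106 was reached

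*Combined protocol and SAP*

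**What the plan says.** - **Synopsis.** Sample size: "The study require the enrollment of at least 110 patients". Study design: a single-arm trial "powered for non-inferiority with respect to historical cohort".
- **Section 4.** The objective is to "Assess the safety of metformin in diabetic patients undergoing coronary angiography in terms of risk of lactic acidosis".
- **Section 5.** The study is called observational and single arm. Non-inferiority is not mentioned.
- **Section 7.1.** The primary endpoint is "An increase of lactic acid of 20% from preprocedural values in patients undergoing coronary angiography without discontinuing metformin".
- **Section 8.1.** In the historical cohort "we observed a mean value of lactic acid of 1.2+0.7 mmol/l" (the plus sign is read as plus-or-minus). The enrolment target then reads "A total of 106 patients in an estimated time of one years are planned to be enrolled". The stated purpose of that number is 90% power, at alpha 0.05, to find lactate 20% higher than before the procedure.
- **Section 11.1.** Student's t, Mann–Whitney or Wilcoxon tests are listed for continuous variables in general, the choice depending on a normality check. A 95% confidence interval is planned for postprocedure lactic acid values.
- **Section 11.2.** The tests are meant "to refuse the null hypothesis of lack of association between metformin continuation and postprocedural increase of lactic acid of 20" (per cent, relative to baseline), at p < 0.05.

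**The concern.** The synopsis and the body give two enrolment targets and two hypotheses, and nothing reconciles them.

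The hypotheses matter more. A non-inferiority claim needs a margin, a comparator and a rule by which the data can exclude harm beyond the margin. The body has none of these: the cohort only supplies a mean and an SD. What is powered and tested is whether lactate rises. Under that test the reassuring outcome is failure to reject, which does not show that a rise is absent or small. As the objective is a safety statement, a reader of the results could not tell from the plan which finding counts as safe.

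The sample size is a second matter. Section 8.1 gives a mean, an SD, an effect, power and alpha, but not the test, its sidedness, the SD of the within-patient change or any attrition allowance. The SD of 0.7 describes lactate levels, whereas a pre-to-post comparison depends on the SD of the change.

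**Working it through.** **Inputs (section 8.1).** Mean 1.2 mmol/L, SD 0.7, rise of 20%, power 90%, alpha 0.05. The rise is 0.20 × 1.2 = 0.24 mmol/L, so the standardised effect is 0.24/0.7 = 0.343.

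**1. Trying to reproduce 106.** Take 0.7 as the SD of change.
- Normal approximation: n = [0.7 × (1.960 + 1.282)/0.24]² = 89.4, so 90 two-sided. With 1.645 in place of 1.960, n = 72.9, so 73 one-sided.
- Paired t-test (noncentral t, noncentrality 0.343 × √n): 92 two-sided, 75 one-sided.

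Neither 106 nor 110 results. 106 appears only after adding something that the plan does not state, for example:
- 15% dropout: 90/0.85 = 105.9, so 106.
- Within-patient correlation rho of about 0.41, with 0.7 as the SD before and after: SD of change = 0.7 × √(2 × 0.59) = 0.760, and [0.760 × 3.242/0.24]² is about 105.5, so 106.
- A two-sided signed-rank test at relative efficiency 0.864: power is 0.898 at 105 and 0.901 at 106.

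The documents do not show which, if any, was used.

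**2. Why a non-significant result would not show safety.** Suppose the observed mean rise is 0.12 mmol/L, with baseline mean 1.2 and the SD of change as shown (all assumed).

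| n | SD of change | 95% CI for the rise | Upper limit as % of 1.2 | p |
|---|---|---|---|---|
| 106 | 0.70 | −0.015 to 0.255 | 21% | 0.080 |
| 110 | 0.70 | −0.012 to 0.252 | 21% | 0.075 |
| 106 | 0.542 | 0.016 to 0.224 | 19% | 0.025 |

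First row: SE = 0.70/√106 = 0.0680, t = 0.12/0.0680 = 1.76, half-width = 1.983 × 0.0680 = 0.135. The null is kept although a 20% rise is not excluded. In the third row the null is rejected although a 20% rise is excluded. The test in section 11.2 and a non-inferiority rule can give opposite answers.

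**3. Power at the two targets.** With SD 0.7 before and after, SD of change = 0.7 × √(2(1 − rho)). Rho is assumed. Two-sided paired t, rise 0.24:

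| rho | SD of change | n = 106 | n = 110 |
|---|---|---|---|
| 0.3 | 0.828 | 84% | 85% |
| 0.5 | 0.700 | 94% | 95% |
| 0.7 | 0.542 | over 99% | over 99% |

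At 106, 90% power needs an SD of change of at most about 0.755, which is rho of about 0.42 or more.

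**4. Power to exclude a 20% rise.** The rule is that the upper 95% limit lies below a fixed 0.24. With a true change of 0, the figures equal those in step 3. With a true rise of 5% (0.05 × 1.2 = 0.06), the distance to the margin is 0.24 − 0.06 = 0.18, and n = 106 gives 60%, 75% and 92% at rho 0.3, 0.5 and 0.7.

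**5. If the cohort were a real comparator.** Assume equal group sizes, SD 0.7, margin 0.24, true difference 0 and one-sided 0.025: n per group = 2 × 89.4 = 178.8, so 179. With 106 per group power is about 70%.

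**The case against.** Several points on the other side have force.

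- **The non-inferiority claim rests on one phrase in the synopsis.** Sections 8.1, 9 and 11.2 all describe looking for an increase. That is so, but the phrase is current text and states what the trial is powered for. A reader might also infer that the plan says a non-significant result will be taken as proof of safety. It does not say so. The risk follows from pairing a safety objective with a test for a rise.
- **106 versus 110 is nearly editorial.** For power this stands: the difference is about one percentage point. At least 110 also does not strictly contradict a calculated need for 106. But no text links the two, so the enrolment target is undefined.
- **106 does have a stated basis.** Largely true: the mean, SD, effect, power and alpha are given. A reader might infer an arithmetic error or an underpowered study. The documents support neither, since 106 exceeds the simple paired t requirement of 92 and several ordinary assumptions lead to it. Nor does the mention of Wilcoxon tests in section 11.1 show that a signed-rank calculation was used, because that sentence covers all continuous variables and depends on a normality check.
- **The endpoint may be read as a per-patient event.** Sections 7.1 and 11.2 permit a yes/no reading, from which one might infer that the sample size belongs to a different endpoint. But section 8.1 works with a mean and SD, and section 11.1 speaks of lactic acid values with confidence intervals. The plan leans to a continuous endpoint, and the wording only needs tightening.

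**Conclusion.** The concern holds in a limited form. The plan claims non-inferiority to a historical cohort, but it has no margin, no cohort comparison and no decision rule, and the null in section 11.2 cannot support the safety objective by being retained. That follows from the text and needs no numerical assumption. The example with p = 0.08 and an upper limit of 21% of 1.2 illustrates it, under an assumed SD of change of 0.70 and baseline mean of 1.2.

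The figure of 106 does not follow from the stated inputs without a further assumption, and that assumption is not recorded. It should be called untraceable. No shortfall is shown: if 0.7 is the SD of change, 106 gives 94% power by two-sided paired t. If 0.7 is the SD of levels, the 90% depends on a correlation that the plan does not give.

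This should be corrected before analysis.

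**What to change.** (a) Use one N in the synopsis and section 8.1, and state any attrition allowance. If 106 evaluable out of 110 was meant, that is 1 − 106/110 = 3.6%.

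(b) Make the synopsis and sections 8.1, 11.1 and 11.2 state one hypothesis. There are three ways:
- Delete the non-inferiority and historical-cohort wording, and state that a non-significant result will not be read as evidence of safety. This is wording only, but it leaves the safety objective without a confirmatory analysis.
- Replace the cohort claim, explicitly, with a within-patient one, since the endpoint is change from baseline. Add to section 11.1 a 95% CI for the pre-to-post change, and conclude that a 20% rise is excluded only if the upper limit is below 20% of the preprocedural mean. This changes the tested hypothesis and adds one analysis.
- Keep the cohort comparison, and state the margin, the cohort size and the analysis. On the assumptions in step 5 an equal-size cohort needs about 179 per group, so 90% power could not be claimed at 106 to 110.

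(c) Reword sections 7.1 and 11.2 to match the mean-change endpoint implied by sections 8.1 and 11.1. Name the paired test, its sidedness and the SD of change (or correlation) behind the N.

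(d) Restate power over a range of correlations such as 0.3 to 0.7 and, if exclusion of a 20% rise is adopted, for a true rise of 0 and of 5%.

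The cost is edits to the synopsis and sections 7.1, 8.1, 11.1 and 11.2. No extra patients are proposed. The downside is that restated power may fall below 90% (60% at rho 0.3 with a true 5% rise) and must be reported.
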